## **7.5 Power and Sample Size Justification**

Approximately 384 events of deaths will be required to achieve 80 % power to detect a treatment difference at the overall two-sided 0.05 significance level after taking the planned efficacy/safety interim look into account. It is expected that approximately 500 patients will be enrolled during an estimated 24-month recruitment period and will then be followed for 12 months to observe a total of approximately 384 death events. In the sample size calculation, it is assumed that the median OS is 12 months for the group with investigational treatment (AEZS-108) and 9 months for the control group (doxorubicin). The sample size calculation has taken the interim analyses into consideration.

Based on published data on the pharmacokinetics of doxorubicin, a sample size of 20 patients for each arm is proposed, to provide a more detailed description than is currently available for the key pharmacokinetic parameters of AEZS-108, doxorubicin, and doxorubicinol. Based on preliminary pharmacokinetic data available from an ongoing study in bladder cancer patients, a variability of AEZS-108 similar to that for doxorubicin may be expected. Since collection of only a limited number of samples over a limited period (about 2-3 terminal elimination half-lives) is feasible within this sub-study, the comparison of the metabolite profiles will be orienting / exploratory / descriptive in nature.

## **8 PHARMACOKINETICS**

A PK sub-study at selected sites and sparse PK sampling at all sites is performed to assess the pharmacokinetics and exposure-response relationships of AEZS-108, doxorubicin and doxorubicinol. A SAP supplement contains all details of non-compartmental analysis that will be performed on the PK sub-study samples and is not part of this main SAP. All details of population PK analysis (using all available PK samples) will be described in a second SAP supplement that is also no part of this main SAP.

## **9 SUMMARIES OF MEASURES OF SAFETY**

Safety analyses will be performed for the safety population. Safety evaluations will be based on the incidence, intensity, and type of adverse events, as well as on clinically significant changes in the patient's physical examination, vital signs, and clinical laboratory results. Safety variables will be tabulated and presented by study drug actually received.

Because there is no pre-specified safety outcome defined in terms of AEs, clinically relevant laboratory parameters, or vital signs, any formal comparisons between the treatment arms with respect to specific safety parameters will be post-hoc.

## 9.1 Adverse Events

Each AE and SAE term recorded on the case report forms (CRFs) will be mapped to a preferred term (PT) using the MedDRA dictionary. The investigator will classify the severity of AEs and SAEs using the NCI CTCAE v4.0 and will assess the relationship of each event to the study treatment.

All AEs and SAEs occurring on study will be listed by treatment drug, center, and patient. Four additional listings will be made: listing of AEs associated with dropout (i.e. Drug withdrawn on CRF page), listing of AEs leading to dose reduction (i.e. Dose reduced on CRF page), listing of AEs with fatal outcome and listing of deaths. AE listings will contain (not limited to): last dose before event (mg/m^2), time on treatment (date of last dose before AE onset – C1D1) and time since last dose (start date of AE – date of last dose before AE onset). The listing of deaths will include for each death case: overall survival (duration), reason for end of treatment, time on treatment (C1D1 – date of last dose), time since last dose (start date – date of last dose) and best response.

The frequency and percentages of patients with treatment-emergent adverse events (TEAEs) will be tabulated by system organ class (SOC) and PT, where treatment-emergent is defined as any AE that;

- occurs after randomization and through the end of the study or up through 30 days after the last dose of study treatment,
- is considered treatment-related (i.e., considered at least possibly related to the study treatment) regardless of the start date of the event, or
- is present before randomization but worsens in intensity or the investigator subsequently considers treatment-related (i.e., considered at least possibly related to any component of the study treatment).

For the purpose of calculating treatment emergence and inclusion in summary tables, incomplete onset dates will be imputed as detailed in Appendix D. If treatment-relatedness is missing, AE will be considered as RELATED. Summaries will display incidence by study drug (AEZS-108 or doxorubicin) received and total incidence, and PTs within each SOC will appear in decreasing order of total incidence. At each level of summarization, a patient will be counted only once for each AE, SOC, or PT experienced within that level.

Related TEAEs, serious TEAEs, Grade 3 or higher TEAEs, Grade 3/4 serious TEAEs, Grade 5 serious TEAEs, related serious TEAEs, related Grade 3 or higher TEAEs, and TEAEs resulting in discontinuation or dose modification of study treatment will be similarly summarized. Summaries of TEAEs by relationship to each of the study treatments will also be prepared.

At each level of summarization, a patient will be counted only once for each AE, SOC, or PT experienced within that level. In the summation for AE severity, within each level of AE, SOC, or PT experienced, the one with the highest severity will be included. In the

summation for AE’s relationship to the study drug, within each level of AE, SOC, or PT experienced, the one with the closest relationship to the study drug will be included.

Several TEAE tables with AEs sorted by PT ( $\geq$  certain cut-off) by decreasing frequency (in the AEZS-108 arm), irrespective of SOC, will be made in addition (see Appendix E – List of Tables/Graphs and Listings).

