In 5.1. Disposition: correct typo in country abbreviations per territory

In 6.1. Prior In 6.1. Treatment for Endometrial Cancer: remove ITT and explain how to analyze

In 6.2. Prior and Concomitant Medications: explain how to analyze

In 6.3. Study treatment exposure: addition of summaries will be made on patients receiving prophylactic antiemetic treatment per treatment cycle, and patients receiving anti-allergic treatment per treatment cycle

Efficacy analysis:

For backward selection in multivariate Cox model and logistic regression model: the significance level to retain a variable in the model will be set at 10%

Sensitivity analysis for ORR: logistic regression models will be used. For ORR, in addition: duration of overall response, duration of stable disease and duration of follow-up will be analyzed

PFS will be analyzed in the subset of patients from MITT that have CR, PR or SD as best overall response

Slight adaptation in description for mixed model approach for analysis of questionnaires

Adverse event analysis:

Clarification of time on treatment (date of last dose before AE onset – C1D1) and time since last dose (start date of AE – date of last dose before AE onset).

Addition: If treatment-relatedness is missing, AE will be considered as RELATED.

Extra AE tables by PT only ( $\geq$  certain cut-off)

Addition of tables for serious TEAEs grade 3/4 and 5

ECG: update of formulas for calculation of QTcB and QTcF

Addition of Appendix E: list of TLFs

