### 4.2 Definition of Time

For the purpose of summarizing efficacy data, time will be defined relative to the date of randomization. Unless otherwise stated, for visits (or events) that occur on or after randomization, time is calculated as:

$$\text{time (days)} = \text{visit date (event date)} - \text{date of randomization} + 1.$$

For visits (or events) that occur prior to randomization, time is calculated as:

$$\text{time (days)} = \text{visit date (event date)} - \text{date of randomization to study treatment}.$$

For listings (such as for adverse events) of the quantity ‘days since first/last dose’ is defined as:

$$\text{days since first/last dose} = \text{event date} - \text{date of first/last dose.}$$

Events that occur on the same day as the first/last dose will therefore be described as occurring zero days from the first/last dose. In most cases, listings will include the number of days since first/last dose of AEZS-108/comparator (doxorubicin).

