Table 14.3.1.17	Grade 3 or higher treatment emergent adverse events (TEAE) (showing PT $\geq$ 2%) – by PT
Table 14.3.1.18	Related grade 3 or higher treatment emergent adverse events (TEAE) – by SOC and PT
Table 14.3.1.19	Related grade 3 or higher treatment emergent adverse events (TEAE) (showing PT $\geq$ 1.8%) – by PT
Table 14.3.1.20	Treatment emergent adverse events (TEAE) resulting in discontinuation of study treatment – by SOC and PT
Table 14.3.1.21	Treatment emergent adverse events (TEAE) resulting in dose reduction of study treatment – by SOC and PT
Table 14.3.1.22	Treatment emergent adverse events (TEAE) resulting in interruption of study treatment administration – by SOC and PT
Table 14.3.2.5	Deaths
Table 14.3.2.6	Deaths on study treatment (within 30 days after last dose of study treatment)
Table 14.3.4.1	Quantitative laboratory test results in SI units, hematology
Table 14.3.4.2	Shift from baseline, hematology
Table 14.3.4.3	Cycle 1 WBC, neutrophils, and thrombocytes, shift from baseline, CTCAE grades
Table 14.3.4.4	Quantitative laboratory test results in SI units, serum chemistry
Table 14.3.4.5	Shift from baseline, serum chemistry

Table 14.3.4.6	Quantitative laboratory test results in SI units, urinalysis
Table 14.3.4.7	Shift from baseline (quantitative), urinalysis
Table 14.3.4.8	Dipstick test results, urinalysis
Table 14.3.4.9	Quantitative laboratory test results in SI units, hormones
Table 14.3.4.10	Shift from baseline, hormones
Table 14.3.4.11	Pregnancy test results
Table 14.3.4.12	Vital signs
Table 14.3.4.13	LVEF summaries
Table 14.3.4.14	LVEF shift from baseline – part 1
Table 14.3.4.15	LVEF shift from baseline – part 2
Table 14.3.4.16	Interpretation of 12 lead ECG results
Table 14.3.4.17	ECG summaries
Table 14.3.4.18	ECG categorical analysis
Table 14.3.4.19	ECOG performance status shift from baseline

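### SAP 9.1: in the deaths listing, time on treatment is reversed and time since last dose does not use the date of death

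*SAP*

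**What the plan says.** SAP 9.1 (Adverse Events) sets out two kinds of listing in one paragraph.

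- **AE listings:** the first quantity is "time on treatment (date of last dose before AE onset – C1D1". The second, whose start date is tied to the AE itself, is "time since last dose (start date of AE – date of last dose before AE onset".
- **Deaths listing (Listing 16.2.7.8 in Appendix E):** "time on treatment (C1D1 – date of last dose), time since last dose (start date – date of last dose". The same sentence also calls for the OS duration of each patient who died.

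SAP 4.2 (Definition of Time) has a general rule for days since first or last dose in listings, introduced with "For listings (such as for adverse events) of the quantity ‘days since first/last dose’ is defined as". The formula is event date minus date of first or last dose, and it adds: "Events that occur on the same day as the first/last dose will therefore be described as occurring zero days from the first/last dose". Its reach is qualified: "In most cases, listings will include the number of days since first/last dose of AEZS-108/comparator (doxorubicin".

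The Document History entry for SAP version 4 reads "Clarification of time on treatment (date of last dose before AE onset – C1D1) and time since last dose". It gives the AE-listing formulas and mentions no matching change to the deaths listing.

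Appendix E also plans Table 14.3.2.6, titled "Deaths on study treatment (within 30 days after last dose of study treatment".

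**The concern.** Two formulas for the same pair of quantities stand one sentence apart and disagree. In the deaths listing the order of subtraction for time on treatment is the opposite of that in the AE listings. For time since last dose, the AE listings tie the start date to the AE, whereas the deaths listing says only *start date*, with nothing to say what started. The date of death, which is the event being listed, is in neither formula.

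The interval from last dose to death helps a reader separate deaths that may be related to treatment from later deaths due to disease. The deaths listing is the natural patient-level check on the 30-day count in Table 14.3.2.6. If its timing column holds something other than time to death, that check cannot be made directly.

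**Working it through.** The plan states no figure to reproduce, so this is a check by date arithmetic.

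**Inputs**
- Listing formulas: SAP 9.1 and 4.2.
- OS in days = date of death − randomization date + 1: SAP 7.1.1.
- 21-day cycles, proposed maximum of nine for AEZS-108: Protocol 6.1.2.
- Treatment to start within 4 days of randomization, as a target and not a guarantee: SAP Appendix A, footnote 13.
- Assumed patient, for illustration only: four undelayed cycles, fatal AE starting 10 days after the last dose, death 18 days after the last dose.

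**Step 1: time on treatment.** With n undelayed cycles, last dose = C1D1 + 21 × (n − 1).
- n = 9: 21 × 8 = 168. As written, C1D1 − last dose = −168; in the AE-listing order, +168.
- n = 4 (the assumed patient): 21 × 3 = 63. As written −63; in the AE-listing order, +63.
- n = 1: both orders give 0.

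The formula as written is therefore never positive. The sign is wrong and the size is right.

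**Step 2: time since last dose.** For the assumed patient the true interval from last dose to death is 18 days.

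| Meaning given to *start date* | Result (days) |
|---|---|
| Onset of the fatal AE | +10 |
| C1D1 | −63 |
| Randomization, 0 to 4 days before C1D1 | −63 to −67 |
| Date of death as the event date (SAP 4.2 rule) | +18 |

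Only the SAP 4.2 rule returns 18. AE onset is the likeliest meaning, since the preceding sentence uses the start date of the AE and the deaths sentence already uses C1D1 for the start of treatment. On that meaning the column stops at onset. It also has no value when a death has no AE record. This can happen: Protocol 7.2.1.2 asks for events up to 28 days after last exposure, and Protocol 8.6.2 allows later survival status to be collected by telephone every 3 months.

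**Step 3: can the interval be recovered from the rest of the listing?** OS − 1 − |time on treatment| = (death − last dose) + (C1D1 − randomization).

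| Randomization to C1D1 (days) | OS (days) | OS − 1 − 63 |
|---|---|---|
| 0 | 0 + 63 + 18 + 1 = 82 | 18 |
| 1 | 1 + 63 + 18 + 1 = 83 | 19 |
| 4 | 4 + 63 + 18 + 1 = 86 | 22 |

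It can, to within the gap between randomization and first dose, and exactly if both dates are known. The approximation is too long by that gap. Near the cut this can matter: a death 28 days after last dose with a 4-day gap would appear as 28 + 4 = 32 days, on the wrong side of 30.

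**The case against.** The strongest reply is that this is a drafting slip in a descriptive listing, with correct definitions elsewhere. SAP 4.2 gives the event-date rule. SAP 6.3 defines duration of exposure in the right order (last dose minus first dose, plus 1). A negative time on treatment for every patient with more than one cycle would be noticed on first output. Table 14.3.2.6 states its own interval in its title. SAP 9 says any formal safety comparison would be post hoc.

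Most of this stands, and it limits the point to a small one. It does not remove it. A programmer would normally follow the formula written for the specific listing, and SAP 4.2 claims to apply only in most cases. A sign error is easy to spot, but the second column is not: a value of +10 in place of 18 looks entirely plausible.

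A reader might infer more than the documents support, in three ways.

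- *That the listing cannot show how soon after dosing a patient died.* Step 3 shows that OS and the size of time on treatment recover the interval approximately.
- *That all of the roughly 384 deaths would fall inside the 30-day window.* This needs *start date* to mean C1D1, a strained reading, and needs Table 14.3.2.6 to be programmed from the listing variable, a link the SAP never states. The 384 are also deaths among randomized patients. SAP 3.2 allows for some who were never treated, and they have no last dose.
- *That disease deaths have no AE start date because they need not be reported as SAEs.* Protocol 7.2.1.1 and 7.2.1.4 waive only the SAE form; such events are still recorded on the CRF. Some late deaths may lack an AE record, but the waiver is not the reason.

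**Conclusion.** The point holds as a specification error in two columns of one safety listing. Time on treatment is reversed for every treated patient, with no change in size. Time since last dose is undefined as written, and under none of the meanings tried for *start date* in Step 2 does it measure the time from last dose to death; only the event-date rule of SAP 4.2, with which it conflicts, does so. In the assumed patient the likeliest reading gives 10 days instead of 18. That difference depends entirely on the assumed dates and is not an estimate for the trial.

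The error does not touch OS, PFS, ORR, any hypothesis test, the type I error rate or the sample size. It is a minor correction, worth making because the formulas are operative instructions and would give wrong values if followed exactly.

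**What to change.** In SAP 9.1, replace the two deaths-listing formulas with:

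- time on treatment = date of last dose − C1D1;
- time since last dose = date of death − date of last dose.

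The first matches the AE listings and the second matches SAP 4.2. SAP 6.3 adds one day to duration of exposure, so nine undelayed cycles would show 168 days in the listing and 8 × 21 + 1 = 169 in the exposure table; a footnote to the listing can say so. Use the second variable to check the listing against the 30-day deaths in Table 14.3.2.6.

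The cost is two corrected formulas and the matching programming specification. No new data are needed: the dates of death, first dose and last dose are already required for OS and exposure.

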6.2.3 Treatment modifications / delay of treatment

Dosage scheme:	60 mg/m ² by intravenous bolus injection, 1-hour intravenous infusion , or according to standard institution procedures, on Day 1 of 21-day (3-week) cycles Note: If the body weight is +/- 10% of the body weight measured at day 1 of the preceding cycle, the body weight measured at day 1 of the preceding cycle may be used for calculating the dose to be prepared in the pharmacy.
Dose adjustment:	(for starting dose)
- Renal function	at GFR below 10 ml/min.: 75 % of calculated dose
- Hepatic function	at serum bilirubin 1.2 to 3.0 mg/100 mL: 50 % of calculated dose; at serum bilirubin > 3.0 mg/100 mL: 25 % of calculated dose
Maximum duration / dose:	up to a cumulative lifetime dose of 550 mg/m ²
Treatment delay:	Subsequent cycles of study treatment should not begin before a patient has recovered to CTCAE Grade 1 from a drug-related adverse event (i.e., causality at least possibly related) that the investigator feels is clinically significant. No treatment delay is required for alopecia or anemia for which supportive therapy should be given according to study sites' clinical practice (see also 6.3.1.3). Re-treatment may be postponed for up to 2 weeks. A patient who has not recovered within 5 weeks after the last dose should be withdrawn and followed up as required. Note that some Prescribing Information cite the criteria used in study NSABP B-15, using a

doxorubicin/cyclophosphamide combination regimen: When necessary, the next cycle of treatment was delayed until the absolute neutrophil count was ≥ 1000 cells/mm³ and the platelet count was $\geq 100,000$ cells/mm³ and nonhematologic toxicities had resolved.

Dose reduction: (for retreatment)
75 % of the starting doses for neutropenic fever/infection.
Doxorubicin dosage must be reduced in case of hyperbilirubinemia as follows:

Plasma bilirubin concentration (mg/dL)	Dosage reduction (from starting dose)
1.2 - 3.0	50 %
3.1 - 5.0	75 %

For further information on treatment modifications, see Sections Dosage and Administration of the Prescribing Information.

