7.2.1.2 Procedures in case of adverse events

Throughout the study, the patient will be questioned and/or examined by the Investigator or his/her designee for evidence of adverse events. The questioning of patients with regard to the possible occurrence of adverse events should be as non-specific as possible.

However, given that it is the site's responsibility to follow up all AEs, specific questions related to previously reported AEs with regard to their resolution or continuation must be asked.

All adverse events occurring during a study have to be documented, regardless of any assumption of a causal relationship, on the respective AE CRF. All events that occurred during the screening period should be documented as medical history. The investigator should ensure, e.g. by telephone call to the trial subject, to record all events that occurred within 28 days after the last exposure to study drug.

Documentation of adverse events includes date of onset and offset, pattern, duration, severity, impact, actions taken, seriousness, and outcome. The investigator should also

evaluate the probability of a causal relationship of the adverse event to the study medication as likely, possible, unlikely, or unrelated. Information provided in the Investigator's Brochure may support this evaluation.

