## **6.3 Study Treatment Exposure**

Study treatment exposure will be summarized by treatment arm in the ITT and safety populations.

The following will be summarized by treatment arm using descriptive statistics:

- number and percentage of patients who received at least one dose ('cycle')
- duration of exposure per patient, calculated as (date of last dose [start date of last cycle] – date of first dose [start date of first cycle] + 1),
- number of doses (cycles) received per patient,
- cumulative dose (in mg/m^2) received per patient,
- patients receiving prophylactic antiemetic treatment per treatment cycle, and
- patients receiving anti-allergic treatment per treatment cycle.

In addition, a table will be made summarizing duration of cycle 1 administration and duration of administration – all cycles combined.

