### **9.5 Cardiac Assessments**

#### **9.5.1 Left Ventricular Ejection Fraction (LVEF)**

LVEF (ECHO or MUGA) data (raw values and change from baseline) will be summarized descriptively (arithmetic mean, standard deviation, median, range interquartile values) by treatment at all available timepoints. In case only a range is specified for an LVEF measurement: use the mid-point (arithmetic mean) of the specified range as the substitute for the not-available point-value when calculating “Raw value result” and “Change”.

Moreover, a shift table will be made analyzing the data at all scheduled post-Cycle 1 Day 1 visits, by worst value post Cycle 1 Day 1 until end of study treatment (EOT) visit, and until end of post therapy follow-up. The following categories will be considered: FROM (%) 50-55, 55-60, 60-65, 65-70, 70-75 and >75 to <35, 40-35, 45-40, 50-55, 55-60, 60-65, 65-70, 70-75, >75. For LVEF-values specified by range the mid-point of the range should be used for the assignment. In addition, at the end of C3, C6, C7, C8, end of treatment and at post-therapy follow-up, number of subjects (and percentage) with absolute decline from baseline of 10% or more or absolute value of LVEF <50%, will be presented. Moreover, cumulatively at any time after C1D1, the following will be assessed: (number of subjects and percentage of):

- Absolute decline by 10% or more,
- Absolute decline by 15% or more,

- Absolute value of LVEF <50,
- Absolute value of LVEF <45%,
- Absolute decline from baseline of 10% or more or absolute value of LVEF <50%,
- Absolute decline from baseline of 15% or more or absolute value of LVEF <45%

A plot with mean LVEF (mean of raw LVEFE values) evolution over time –by treatment arm (including indication of number of patients present at each time point) will also be made.

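### Adverse events are summarised only as the percentage of patients ever affected, so at equal risk per cycle the arm treated longer shows the higher percentages

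*SAP*

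**What the plan says.** **Adverse events.** SAP 9.1 states: "The frequency and percentages of patients with treatment-emergent adverse events (TEAEs) will be tabulated by system organ class (SOC) and PT". A patient counts once per AE, SOC or PT. The related, serious, grade 3 or higher and discontinuation tables follow the same pattern, and the 22 TEAE tables in SAP Appendix E (14.3.1.1 to 14.3.1.22) are of this kind.

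**Collection.** Protocol 7.2.1.2 asks the investigator "to record all events that occurred within 28 days after the last exposure to study drug". Protocol 7.2.1.4 ends SAE reporting 4 weeks after the last dose, except that impaired cardiac function is reportable for 1 year. The TEAE window in SAP 9.1 names two end points joined by 'or': the end of the study, or 30 days after the last dose.

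**Exposure.** SAP 6.3 summarises duration, cycles and cumulative dose by arm. SAP 9.1 puts time on treatment into the AE listings. Neither enters an AE summary. Protocol 6.1.2 caps AEZS-108 at 9 cycles, and Protocol 6.2.3 allows doxorubicin "up to a cumulative lifetime dose of 550 mg/m"².

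**LVEF.** Tests are scheduled at the end of cycles 3 and 6 and at end of therapy (Protocol 8.4.5 and 8.5). Cycle 7 and 8 tests are only recommended, and results are recorded only if abnormal. Later tests need signs of cardiac failure (Protocol 8.6). SAP 9.5.1 gives a by-visit count for one composite (decline of 10% or more, or LVEF below 50%), values and changes at all timepoints, a shift table, and a mean plot with numbers present. It then lists six criteria for which "cumulatively at any time after C1D1, the following will be assessed".

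**The concern.** Comparing safety is a secondary objective, and PFS superiority is a key secondary test (SAP 7.4). Progression ends treatment, so a drug that delays progression keeps patients on treatment, and under AE observation, for longer. A once-per-patient percentage then rises with exposure even when the risk per cycle is the same. If AEZS-108 works, part of its efficacy would be read as toxicity. If it is stopped sooner, the same tables would hide a higher risk per cycle.

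The 15% decline and <45% LVEF criteria correspond to the cardiac-toxicity withdrawal criteria in Protocol 5.3. SAP 9.5.1 names them only as cumulative percentages. The shift table has bands below 45%, so part of that count could be pieced together, but not the 15% decline. Nothing links a crossing to cumulative dose, although the protocol limits doxorubicin by lifetime dose.

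**Working it through.** **The plan's own figures.** The documents give no expected AE incidence and no expected number of cycles by arm, so there is no stated figure to reproduce on this point. The nearest is SAP 7.5: "Approximately 384 events of deaths will be required to achieve 80 % power to detect a treatment difference", where "it is assumed that the median OS is 12 months for the group with investigational treatment (AEZS-108) and 9 months for the control group". This gives HR = 9/12 = 0.75. With (1.960 + 0.842)² = 7.849:
- Schoenfeld: 4 × 7.849 / (ln 0.75)² = 379.4, so 380 deaths.
- Freedman: (1.75/0.25)² × 7.849 = 384.6, so 385 deaths.

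The plan's 384 is reproduced and is not affected by this point. The 0.75 is borrowed below as one possible ratio of stopping hazards.

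**Model (assumptions).** Risk p of a first event in each cycle, the same in both arms. Probability q of going on to the next cycle. Cap of 9 cycles in both arms (550/60 = 9.17 for doxorubicin at full dose).
- Mean cycles = Σ qᵏ, k = 0 to 8.
- Cycles at risk before a first event, R = Σ [q(1−p)]ᵏ, k = 0 to 8.
- Crude percentage ever affected = p × R.
- Exposure-adjusted rate = first events / cycles at risk = pR/R = p, so its ratio between arms is exactly 1.00.

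**Inputs for q.** The only persistence figure in the documents is Protocol 1.2.2: 28 of 43 (65.1%) completed 6 cycles of AEZS-108 in Phase II. This gives q⁵ = 0.651, so q = 0.918. Those patients were less pretreated (8 of 43 had prior platinum/taxane, Protocol 1.3), so q = 0.85 is also shown. For doxorubicin, q is raised to the power 1/h, where h is the assumed ratio of stopping hazards (AEZS-108 to doxorubicin).

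| Scenario | Mean cycles, AEZS-108 v dox | p = 3% | p = 5% | p = 10% | Crude ratio, p = 3% to 10% |
|---|---|---|---|---|---|
| 1: q = 0.918, h = 0.75 | 6.5 v 5.9 | 17.7 v 16.2% | 27.7 v 25.4% | 47.2 v 43.7% | 1.09 to 1.08 |
| 2: q = 0.918, h = 0.5 | 6.5 v 5.0 | 17.7 v 13.7% | 27.7 v 21.7% | 47.2 v 37.9% | 1.29 to 1.24 |
| 3: q = 0.85, h = 0.5 | 5.1 v 3.4 | 14.1 v 9.6% | 22.2 v 15.4% | 38.7 v 28.0% | 1.46 to 1.38 |

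Worked cell (scenario 1, p = 5%): R = 5.532 for AEZS-108 and 5.074 for doxorubicin. Then 0.05 × 5.532 = 27.7%, 0.05 × 5.074 = 25.4%, and the ratio is 1.09. At p = 1% in scenario 3 the ratio is 1.49. With h = 1 it is 1.00 throughout. An event that can occur only in cycle 1 also gives 1.00, because every treated patient has a cycle 1.

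**Reverse check.** In scenario 2, a per-cycle risk of 2.3% on AEZS-108 against 3.0% on doxorubicin (about 24% lower) gives the same crude percentage, 13.7%, in both arms. The planned tables would show no difference.

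**Limit of the model.** Collection to 28 days after the last dose covers the last 21-day cycle plus one week. Ignoring that extra week for every patient overstates the ratios slightly.

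**The case against.** The strongest reply is that the distortion may be small. Both arms are capped near 9 cycles, no expected duration by arm is stated, and the scenarios anchored on the one persistence figure give ratios of about 1.1 to 1.3. Exposure is tabulated by arm beside the AE tables. SAP 9 declares any formal safety comparison post-hoc, so no type I error claim is at stake. All of this stands. It limits the size, but it does not supply an AE summary that allows for exposure. In an open-label trial, an adjustment chosen after results are known carries less weight than one fixed beforehand.

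A reader might go further and infer that LVEF crossings too appear only as 'ever' percentages, unrelated to cycle. SAP 9.5.1 does not support that: it has the by-visit composite, changes at all timepoints, the shift table and the mean plot. A reader might also infer that safety capture stops with treatment. It does not: AEs run about four weeks further, every patient has an end-of-therapy LVEF, impaired cardiac function is reportable for a year, and signs of cardiac failure trigger LVEF testing in follow-up.

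A full time-to-first-crossing analysis of LVEF by cycle is tempting but would be unreliable. Normal cycle 7 and 8 results are not recorded, and LVEF falls are themselves withdrawal criteria, so the end of testing is informative.

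**Conclusion.** The point holds for adverse events. Once-per-patient percentages are the only planned summary, and time at risk depends on time on treatment. At equal risk per cycle, the crude ratio runs from about 1.08 (6.5 v 5.9 cycles) to about 1.5 (5.1 v 3.4 cycles). These durations, the constant per-cycle risk and the stopping-hazard ratios are assumptions. The documents do not support a firm prediction that AEZS-108 will look more toxic, because the direction and size depend on durations not yet known.

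For LVEF the gap is narrower: the 15% decline and <45% criteria are named only as cumulative percentages, and crossings are not related to cumulative dose. This is a worthwhile addition to the safety analysis. It does not affect the primary analysis or the 384-death target.

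**What to change.** **SAP 9.1 and Appendix E.** Keep the crude tables. Add, by arm, patients with a first event per 100 patient-cycles at risk, with 95% CI, for any, related, serious, grade 3 or higher and cardiac TEAEs. Define time at risk by one stated TEAE window in place of the present two, and reconcile it with the 28-day collection period. SAP 9.1 also counts treatment-related events as TEAEs whatever their start date. Show any that fall outside the window separately, so that numerator and denominator match.

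**SAP 9.5.1.** Extend the by-visit table to the 15% decline and <45% criteria, with the number of patients tested at each visit and, within arm, cumulative dose at first crossing. Limit by-cycle denominators to the scheduled cycle 3, cycle 6 and end-of-therapy tests. Show the reasons testing ended, by arm.

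**Cost.** SAP wording and a few more tables, from dose dates, AE onset dates and scheduled LVEF results already collected. Per-cycle rates assume a roughly constant risk. They can mislead for events concentrated in early cycles or rising with cumulative dose, which is why the crude tables stay and dose at first crossing is shown. No dose or clinical rule changes.
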